4.4 Study Data Collection and Measures

4.4.1 Medical Data Collection (Aim 1)

Because patient self-report about medical history can occasionally differ from the data on the same items in patients' charts (e.g., treatments received), we will collect the following data on enrolled patients through medical chart review: date of diagnosis and disease stage, dates and types of treatments and surgeries received for breast cancer, current treatment status, current medication use (including endocrine therapies), and current menopausal status (See Medical Records Data Collection Form in Appendix). The data abstraction will be performed by [name], a Nurse Practitioner and Co-Investigator on our study, or another member of the study team trained or supervised by [name], and entered into our de-identified databases. This medical chart review is documented in the consent form.

4.4.2 Self-Report Data Collection (Aim 1). An overview of study measures and collection time points for participants in Aim 1 (the pilot trial), including number of items in each scale, is in **Table 3**. After consenting, patients and partners will complete pre- and post-intervention outcome measures through a web portal on their home computers using RedCap.

4.4.2.1 Overview of Self-Report Data Collection (Aim 1).

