4.5.1 Overview of Randomization and Intervention Conditions (Aim 1)

Couples will be randomized with an allocation ratio of 2:1 to either the IE or the Educational Control (Living Healthy Together) condition, in order to maximize data generated on the active condition, with stratification by age at diagnosis (≤ 45 vs. > 45) using the age obtained by patients during the screening. Because of the broad intimacy targets of this intervention, outcomes may not differ by menopausal status and therefore we will not stratify by this variable. However, because sexual function can differ by menopausal status, we will investigate menopausal status as a possible moderator of outcome in the intervention group for future research.

Randomization will occur once both members of the couple have consented, completed baseline surveys, and are scheduled for their first intervention session. At this time, the couple will be sent sealed study materials along with the instructions to leave the envelopes sealed until they “meet” with their interventionist for session 1. It is important to keep the study condition a secret from participants until Session 1 to reduce the chances for unequal drop-out prior to Session 1, which could occur if patients/partners are more motivated to attend sessions in one study group as opposed to the other.

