3 (60 min)	Problem-solving and Changing Thoughts	1. Impact of BC on body image 2. Using problem-solving vs acceptance 3. Current physical/medical treatments 4. Model of cognitions and intimacy 5. Broadening range of intimate activities	1. Identify/restructure inflexible thoughts 2. Emotional intimacy through engagement in activities 3. Coping with sexual difficulties 4. Behavioral physical intimacy coping	1. Novel intimate activity 2. Sensate focus
4 (60 min)	Planning Ahead and Preparing for Challenges	1. Review of skills and education 2. Evaluate progress toward goals 3. Plan for continued skill practice 4. Anticipate/ plan for challenges	1. Goal-setting 2. Behavioral physical intimacy coping	1. Complete post-intervention measures

4.5.3 Educational Control Condition (Aim 1). The Educational Control condition (called Living Healthy Together or LHT) is a stringent control condition which equates with the active condition for time and attention from a therapist, and

receiving education from a credible source. However, in contrast with the IE condition, LHT focuses on education and support rather than skills training (See Appendix for outline) and it also does not include specific education on sexuality or intimacy. Like the IE condition, the LHT condition follows a structured outline for each session though the discussions can depend on participants' interests and the sessions are designed to last as long as IE sessions.

Topics to be discussed include breast cancer and its treatments (e.g., staging, common treatments, side effects), sleep and energy, stress and stress management, nutrition/diet. All of these topics are relevant to sexual function⁷⁵ and therefore make up an appropriate and highly credible control condition for patients screened for sexual concerns. Unlike in the IE condition, participants in LHT will not be explicitly encouraged to engage in particular activities or management strategies but rather will be encouraged to read the materials given to them provided at each session. Their engagement with the material will be assessed at each session using the Materials Review Form, just as in the IE condition.

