6.0 Potential Benefits to Participants

While we hope that the Intimacy Enhancement intervention will benefit patients and partners, there may be no direct benefit to the study participants. It is possible that the Intimacy Enhancement intervention may address patients' sexual concerns and therefore have a beneficial effect on patient and partner sexual quality of life outcomes, relationship outcomes, and on patient psychosocial outcomes. Couples in the Educational Control condition may also benefit from having the support of a professional for an equivalent length of time and from the educational material provided. Findings from the pilot trial will inform the design of a larger multi-site trial which has the potential to improve patient health and quality of life, once disseminated. Findings from the developmental aim may inform future research on interventions that may be well-suited to addressing the sexual concerns of a large number of breast cancer survivors. The minimal risks to subjects are reasonable in relation to potential benefit in improving the health and quality of life of women with breast cancer, especially in light of the dearth of available evidence-based interventions addressing sexual concerns for this population.

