13.1.2. Analyses

13.1.2.1. Feasibility. Analyses will be descriptive. We aim for accrual at a rate of 30% to match our prior study,⁴² but a rate over 20% will be acceptable. Attrition at levels greater than those found by similar studies⁴⁷ (e.g., 30%) will be considered unfeasible. 80% of participants completing the 4 sessions is considered adequate.

13.1.2.2. Acceptability. Analyses will be descriptive. Adequate acceptability of the study will be indicated by a group median score ≥ 28 on the CSQ-8,⁷⁶ representing a fairly high score across a range of studies, including a behavioral marital therapy randomized controlled trial.⁷⁷

13.1.2.3. Preliminary efficacy. Preliminary efficacy of the IE intervention on patient and partner sexual outcomes, patient and partner relationship outcomes, and patient psychosocial outcomes will be established using an effect size calculation method that is appropriate for small sample sizes³⁴ that our team has employed previously.^{34,49} First, pre-post changes scores are calculated for each participant. Second, the between-group effect size is calculated by subtracting the mean control group change score from the mean IE group change score. This difference is then divided by the standard deviation of the pooled change score. Given that multilevel dyadic analyses are questionable in small sample sizes,⁷⁸ we will consider dyadic analyses, including actor-partner effects,⁷⁹ in the planned R01.

Because our primary goal through the analyses for this aim is to generate effect sizes for a larger planned study, we will conduct the analyses described above using data from study completers. However, we will also attempt to obtain post-treatment surveys even for couples who have dropped out of the study during the intervention phase, to allow us to conduct intent-to-treat analyses. Patients without any post-treatment data will have baseline data used in these analyses.

13.2. Statistical Analyses for Aim 2

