13.2.4. Sample Size Calculations

The objective of this study is to pilot test the newly adapted Intimacy Enhancement study and to allow us to calculate effect sizes that will inform a larger R01 trial that is expected to follow from this study. We selected 30 couples to participate in this trial because it is a large enough sample to provide ample pilot data while maintaining adequate feasibility in the time allotted. Further, we have chosen a 2:1 allocation to the Intimacy Enhancement condition, which allows us to gather greater information from participants in this condition, our primary interest, relative to the Couple Education condition.

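### Examining menopausal status in the IE arm alone can show a predictor of change within IE, not a moderator of the treatment effect

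*Combined protocol and SAP*

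**What the plan says.** Section 4.5.1 randomizes couples 2:1 to IE or the Educational Control (LHT), stratified by age at diagnosis. Menopausal status is not a stratification factor, on the ground that "outcomes may not differ by menopausal status and therefore we will not stratify by this variable". The next sentence gives the reason for still looking at status, "because sexual function can differ by menopausal status", and then the plan: "we will investigate menopausal status as a possible moderator of outcome in the intervention group for future research".

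Section 13 contains no subgroup, interaction or moderator analysis. For preliminary efficacy, section 13.1.2.3 computes a pre-post change score for each participant, and "the between-group effect size is calculated by subtracting the mean control group change score from the mean IE group change score". Section 4.4.1 lists the items taken from the charts of enrolled patients, "and current menopausal status" among them, without restriction by arm. Section 13.2.4 explains the 2:1 ratio as a choice "which allows us to gather greater information from participants in this condition, our primary interest".

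**The concern.** In a randomized comparison, a moderator is a variable across which the treatment effect differs. The plan's own treatment effect is a difference between arms. The menopausal analysis, as placed, has no control term, so it addresses a different quantity: whether change among IE patients varies with status. The stated reason for the analysis is prognostic (function can differ by status), which is a reason to expect a predictor and makes the two easy to confuse.

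What is at stake is narrow. The result is intended for future research, and the pilot is meant to inform a larger trial. If a within-IE difference were passed on under the name of moderation, it could be taken as evidence that IE works better in one group, and might influence stratification or targeting later. This analysis cannot carry that conclusion.

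**Working it through.** The documents give no figure for this analysis, so there is nothing to reproduce. The check is first algebraic, then a calculation of how precise the alternative would be.

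**What each contrast estimates.** Take two status groups, pre- and postmenopausal (the two-group form is an assumption). Let D_IE be mean change in premenopausal minus postmenopausal IE patients, and D_LHT the same difference in the control arm.

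- IE-only contrast: D_IE.
- Moderation: (IE − LHT among premenopausal) − (IE − LHT among postmenopausal) = D_IE − D_LHT.

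The two agree only if D_LHT = 0. Two illustrations with an assumed 0.8 SD:

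- Status predicts change equally in both arms: D_IE = 0.8 and D_LHT = 0.8. IE-only shows 0.8; moderation is 0.8 − 0.8 = 0.
- Status makes no difference within IE but does in the control arm: D_IE = 0 and D_LHT = −0.8. IE-only shows 0; moderation is 0 − (−0.8) = 0.8.

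**Inputs for precision.** From the documents: 30 couples at 2:1, hence 20 IE and 10 LHT patients (sections 4.5.1 and 13.2.4); 30% as the example attrition limit (section 13.1.2.1). Assumed: change-score SD of 1 in every cell, and the same split in both arms, at 50:50, 70:30 or 80:20.

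**Formulas.** Var(IE-only) = sum of 1/n over the two IE cells. Var(two-arm) = sum of 1/n over all four cells. 95% half-width of the two-arm contrast = t × SE, with 30 − 4 = 26 degrees of freedom and t = 2.056.

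| Split | IE cells | LHT cells | Var IE-only (SE) | Var two-arm (SE) | Two-arm 95% half-width |
|---|---|---|---|---|---|
| 50:50 | 10/10 | 5/5 | 0.200 (0.447) | 0.600 (0.775) | 1.59 |
| 70:30 | 14/6 | 7/3 | 0.238 (0.488) | 0.714 (0.845) | 1.74 |
| 80:20 | 16/4 | 8/2 | 0.3125 (0.559) | 0.9375 (0.968) | 1.99 |

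With 30% attrition in each arm (14 IE and 7 LHT; 21 − 4 = 17 degrees of freedom; t = 2.110), the two-arm SE is 0.926 at 50:50 and 1.157 at 80:20, so the half-width is 1.95 to 2.44 SD. The smaller control cell at 80:20 then averages 7 × 0.2 = 1.4 patients.

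**When the two-arm contrast is the better estimate.** As an estimate of moderation, IE-only has mean squared error Var(IE-only) + D_LHT². It equals the two-arm error when D_LHT = √(Var two-arm − Var IE-only): √0.400 = 0.63, √0.476 = 0.69 and √0.625 = 0.79 SD for the three splits. Below those values the IE-only figure is, on average, closer to the moderation effect.

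**The case against.** The strongest reply is about wording. The plan says moderator of outcome in the intervention group, not moderator of the treatment effect. Read literally, that is already a within-IE predictor analysis with one loosely used word. This reading is available, and it keeps the point small. It does not remove it: moderator has a specific meaning in a randomized trial, and nothing in section 13 tells the reader which meaning applies.

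The second reply is that the alternative is no better in practice. This stands in large part. The two-arm contrast has 1.73 times the standard error of the IE-only contrast. Unless the control-arm difference by status exceeds about 0.63 to 0.79 SD, it also has the larger mean squared error. A reader might infer that adding the control arm would give fewer false leads; the figures do not support that. What it gives is an estimate of the right quantity with its uncertainty visible. Imprecision in that contrast does not turn the IE-only difference into an estimate of moderation.

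Third, control cells of one or two patients carry almost no information, and an SD from a single patient does not exist. That is correct, and it limits what should be tabulated.

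Fourth, the analysis is exploratory, and a focus on IE is deliberate and reasonable. Both are accepted; no decision rule or sample size in the plan depends on it.

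**Conclusion.** The point holds as one of interpretation. Followed as written, the analysis in section 4.5.1 can show whether menopausal status predicts change among IE patients. It cannot support a statement that the effect of IE over LHT differs by status. This follows from the algebra and needs no assumption about the data. The half-widths of about 1.6 to 2.0 SD (up to about 2.4 SD with 30% attrition) depend on the assumed unit SD and splits.

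Two stronger readings are not supported. One is that the planned result will be biased. Section 6.0 says "Couples in the Educational Control condition may also benefit from having the support of a professional for an equivalent length of time", and section 4.5.3 says of the control topics that "All of these topics are relevant to sexual function". Change without IE content is therefore possible, but neither section says that it differs by menopausal status. The other is that the trial's main results are compromised. Feasibility, acceptability and the between-group effect sizes in section 13.1.2 do not depend on this analysis. It is a minor point, worth correcting because correction is nearly free.

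**What to change.** In section 4.5.1, with a matching line in section 13.1.2.3:

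- Describe any difference by menopausal status within IE as an exploratory predictor of change within IE, and draw no moderation conclusion from it.
- Show mean pre-post change and cell size by status for both arms, as description, with SDs only where cell size allows.
- If moderation is discussed at all, base it on the difference in IE-minus-LHT change between status groups with its 95% CI, labelled descriptive. If no moderation statement is made, this contrast can be left out.

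The cost is about two sentences. No new data are needed, since status is abstracted for enrolled patients and change scores are computed in both arms, and no regression model is required. The drawback is that control means by status will be rough, and the optional contrast will exclude only very large differences. The text should say so.

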4.5.1.2 Interventionists (Aim 1)

All sessions will be conducted by an experienced and trained counselor. The interventionists have Master’s degrees or above (doctorate) in social work or counseling/psychology and are either licensed to engage in clinical services or have equivalent educational background and/or experience. Interventionists also have years of relevant clinical experience including conducting CBT. Some of the current interventionists have also had experience conducting couple therapy sessions on [name]’s couple-based studies and are thus familiar with utilizing intervention manuals in conducting interventions as part of a research study. Interventionists will be trained to deliver both types of intervention sessions through an in-person training workshop or viewing a recording of the in-person training workshop that will include review of couple therapy approaches and about the topic area, review of study intervention manual and patient handouts, and interactive role plays with feedback. The precise content of each interventionist’s training procedures could differ slightly depending on their prior experience and comfort with the material. Interventionists may also listen to session recordings as a part of their training. All interventionists will be certified by the PI as adequately trained prior to scheduling them for sessions with intervention participants. Regular supervision sessions among the interventionists led by [name], the PI and developer of the IE intervention, will be held to ensure adequate quality of the delivered interventions. All supervision sessions are confidential; no identifiable information about participants is retained in supervision records. The quality assurance procedures regarding the delivery of the intervention are described further in section 16.0.

4.5.1.3 Intervention Format (Aim 1)

All sessions will be delivered over the telephone. In our prior work, participants found the telephone-based format desirable for addressing the intimate topic of sexuality and many preferred it over face-to-face.⁶⁴ This format is also well-suited to reach post-treatment and long-term breast cancer survivors, who report the greatest interest in obtaining help for their sexual concerns,⁷⁰ and to whom eligibility for this study is limited. Audio calls will be made using Skype (not video calls), cell phone, or landline service to the couple's preferred mobile or landline phone (no Skype username or subscriptions needed for couples) using speakerphone. All sessions will be recorded, and these audio recordings destroyed when the study is completed.

4.5.2 Intimacy Enhancement (IE) Intervention (Aim 1). The proposed IE intervention content is outlined in Table 5 (See Appendix for a draft outline of the intervention)^{41,49} and includes four structured sessions. A couple-based intervention is ideal for breast cancer survivors because most survivors want to address their sexual concerns in a couple-based format²⁵ and because couple-based interventions are more effective at improving sexual outcomes in this population.^{30,71} The first session is intended to be longer (approximately 75 minutes) because of the nature of the first session as involving rapport-building, information gathering, and providing education. Subsequent sessions will last approximately 60 minutes.

The IE intervention includes both educational content and cognitive and behavioral skills training with the aim of reducing sexual distress and avoidance, increasing coping skills of both patients and partners, and improving physical and emotional intimacy. A unique feature of this intervention is that it addresses a range of both physical and emotional intimacy targets, such as loss of sexual interest and activity, and behavioral couple-based skills to adjust to sexual changes (e.g., sensual touching). Such skills are critical elements of successful programs addressing sexual concerns for breast cancer survivors⁷¹ and [name] has published previously on an Intimacy Enhancement intervention teaching these skills.^{64,65} Techniques are also included from (a) sex therapy, including sensate focus (sensual touching exercises),⁷² (b) couple therapy (e.g., communication skills),⁷³ and (c) cognitive behavioral therapy (e.g., restructuring negative/inflexible thoughts).^{51,74} A cornerstone of the IE intervention is an approach to coping with sexual difficulties proposed previously by the PI that emphasizes flexibility in thoughts and behaviors.⁵¹ Participant handouts will reinforce educational topics, provide opportunities for interactive exercises, or otherwise reinforce skills learned during the sessions. Weekly home behavioral skills practice are reviewed at the beginning of each session, including proceeding through a stepped set of sensate focus exercises with the goal of reducing avoidance of sensual behaviors and increasing intimacy.

Session	Topic	Education Topics	Skills	Home practice
1 (75 min)	Understanding Impact of BC on Sex and Intimacy	1. Models of female sexual function 2. Effects of BC on sex and intimacy 3. Identify and normalize problems 4. Introduce sensate focus	1. Goal-setting 2. Behavioral physical intimacy coping 3. Coping with sexual difficulties	1. Read educational material 2. Sensate focus
2 (60 min)	Communication about Sex/ Intimacy	1. Effective communication 2. Communicating about intimacy 3. Feedback on in vivo practice	1. Communication 2. Behavioral physical intimacy coping	1. Communication practice 2. Sensate focus
3 (60 min)	Problem-solving and Changing Thoughts	1. Impact of BC on body image 2. Using problem-solving vs acceptance 3. Current physical/medical treatments 4. Model of cognitions and intimacy 5. Broadening range of intimate activities	1. Identify/restructure inflexible thoughts 2. Emotional intimacy through engagement in activities 3. Coping with sexual difficulties 4. Behavioral physical intimacy coping	1. Novel intimate activity 2. Sensate focus
4 (60 min)	Planning Ahead and Preparing for Challenges	1. Review of skills and education 2. Evaluate progress toward goals 3. Plan for continued skill practice 4. Anticipate/ plan for challenges	1. Goal-setting 2. Behavioral physical intimacy coping	1. Complete post-intervention measures

4.5.3 Educational Control Condition (Aim 1). The Educational Control condition (called Living Healthy Together or LHT) is a stringent control condition which equates with the active condition for time and attention from a therapist, and

receiving education from a credible source. However, in contrast with the IE condition, LHT focuses on education and support rather than skills training (See Appendix for outline) and it also does not include specific education on sexuality or intimacy. Like the IE condition, the LHT condition follows a structured outline for each session though the discussions can depend on participants' interests and the sessions are designed to last as long as IE sessions.

Topics to be discussed include breast cancer and its treatments (e.g., staging, common treatments, side effects), sleep and energy, stress and stress management, nutrition/diet. All of these topics are relevant to sexual function⁷⁵ and therefore make up an appropriate and highly credible control condition for patients screened for sexual concerns. Unlike in the IE condition, participants in LHT will not be explicitly encouraged to engage in particular activities or management strategies but rather will be encouraged to read the materials given to them provided at each session. Their engagement with the material will be assessed at each session using the Materials Review Form, just as in the IE condition.

